The total study duration for subjects who complete this Phase 3 study and who fail to qualify for participation in the OL-LTE study, or who qualify to participate in the OL-LTE study but elect not to enroll in that study is up to 13 weeks in total (including up to 30 days screening, 8 weeks treatment, and a 1-week follow-up period).

Functional Outcomes and Quality of Life Analysis:

Change from Baseline in [REDACTED]

[REDACTED] Peak Pruritus-NRS scores will be analyzed using an ANCOVA model with treatment as a main effect, and baseline as a covariate.

Pharmacokinetic Analyses:

Plasma concentration data will be listed and summarized by study visit.

Schedule of Assessments

Table 1: Schedule of Assessments

Procedures and Assessment	Screening	Baseline	Double-Blind Vehicle-Controlled Treatment Phase						FU ^a	ET ^b
	V1	V2	V3	V4	P/C ^c	V5	P/C ^c	V6	V7	NA
	Day -30 to Day -1	Day 1	Week 1 Day 8 (±2 d)	Week 2 Day 15 (±2 d)	Week 3 Day 22 (±2 d)	Week 4 Day 29 (±2 d)	Week 6 Day 43 (±2 d)	Week 8 Day 57 (±2 d)	Week 9 Day 64 (±2 d)	NA
Informed consent	X									
Demographics	X									
Fitzpatrick skin type	X									
Medical history ^d	X	X ^e								
Assess/confirm eligibility	X	X								
Serum/urine pregnancy test (WOCBP) ^f	X	X ^g					X		X	X
Brief physical examination ^h	X	X					X		X	X
Vital signs ⁱ	X	X	X	X			X		X	X
ECG ^j		X					X		X	X
Blood sample for clinical laboratory tests ^k	X	X ^l					X		X	X ^m
Urinalysis	X	X ⁿ					X		X	X ^m
PK sample ^o							X		X	
Subject randomization		X								
Photograph representative of disease area ^p		X		X			X		X	
Adverse events	X	X	X	X	X	X	X	X	X	X
Concomitant medication	X	X	X	X	X	X	X	X	X	X
Investigator Assessed										
vIGA-AD TM score ^q	X	X	X	X			X		X	X
%BSA affected ^q	X	X	X	X			X		X	X
EASI ^q	X	X	X	X			X		X	X
LTS ^r		X	X	X			X		X	X
Completed by Subject or Caregiver										

Procedures and Assessment	Screening	Baseline	Double-Blind Vehicle-Controlled Treatment Phase						FU ^a	ET ^b
	V1	V2	V3	V4	P/C ^c	V5	P/C ^c	V6	V7	NA
	Day -30 to Day -1	Day 1	Week 1 Day 8 (±2 d)	Week 2 Day 15 (±2 d)	Week 3 Day 22 (±2 d)	Week 4 Day 29 (±2 d)	Week 6 Day 43 (±2 d)	Week 8 Day 57 (±2 d)	Week 9 Day 64 (±2 d)	NA
PP-NRS (pre-dose) ^s		X	X	X		X		X	X	X
LTS ^r		X	X	X		X		X		X
Dispense (D)/collect (C) diary ^t		D	C/D	C/D		C/D		C		C
Review subject diaries for treatment compliance			X	X		X		X		X
Dispense (D)/Collect (C) study drug		D	C/D	C/D		C/D		C		C
Review instructions for study drug application ^u		X	X	X	X	X	X			

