7.6 Visit 6; Week 8 (Day 57 ±2 Days)

The following procedures and assessments will be performed at Visit 6:

- Urine pregnancy test (females of child-bearing potential)
- Brief physical examination
- Vital signs measurement
- Blood sample collection for clinical laboratory tests (serum chemistry, hematology, diagnostic tests)
- Urinalysis
- Blood sample collection for PK analysis (at a subset of study sites only)
- ECG recording (at a subset of study sites only)
- Photography of a representative area of the subject's disease area (at a subset of study sites only)
- vIGA-AD™ score (excluding subject's scalp)
- %BSA affected calculation (excluding subject's scalp)
- EASI (excluding subject's scalp)
- [REDACTED]
- [REDACTED]
- PP-NRS
- [REDACTED]
- [REDACTED]
- Investigator-assessed LTS
- Subject (or caregiver)-assessed LTS
- AE recording
- Concomitant medication recording
- Collect subject diaries
- Review subject diaries for treatment compliance
- Collect study drug
- Enrollment in OL-LTE study (optional)

7.7 Phone Contact at Weeks 3 (Day 22 ±2 Days) and 6 (Day 43 ±2 Days)

Subjects or their caregivers will be contacted by phone at Weeks 3 and 6 to review study drug application instructions and to record AEs and concomitant medication use. Subjects should be reminded to complete their daily diary and bring it with them to the next clinic visit.

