7.8 Follow-Up Visit 7; Week 9 (Day 64 ±2 Days)

Subjects who complete Visit 6/Week 8 but do not enroll in the OL-LTE study will return to the study site at Week 9 to complete Follow-Up assessments as follows:

- Brief physical examination

- Vital signs measurement
- If needed, blood sample collection for clinical laboratory tests
- If needed, urinalysis
- vIGA-AD™ score (excluding subject's scalp)
- %BSA affected calculation (excluding subject's scalp)
- EASI (excluding subject's scalp)
- [REDACTED]
- [REDACTED]
- PP-NRS
- [REDACTED]
- [REDACTED]
- AE recording
- Concomitant medication recording

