The imputation models may be modified based on the actual data if there is an issue in model convergence.

Sensitivity analyses of the primary and secondary endpoints will be performed using MI (non-estimand), last observation carried forward (LOCF), observed cases (OC) (i.e., no imputation), and imputing missing data as Treatment Failures (TF). Only missing data up to Week 8 will be imputed. Missing data at the Week 9 Follow-up visit will be summarized as OC only.

LOCF: The last observed value will be carried forward for any subsequent missing values. Baseline values will not be carried forward. Unscheduled visits will be included.

TF: missing data will be imputed as treatment failures for responder endpoint.

Missing functional outcomes, quality of life endpoints or safety endpoints will not be imputed.

Average weekly PP-NRS scores will be calculated for all nominal visits as the average of 7 daily post-baseline PP-NRS scores prior to and including the values assessed on the visit date. If daily PP-NRS scores are missing for more than 3 days in a 7-day period, the average weekly PP-NRS score will be set to missing. If two or more scores are reported on the same day, the maximum score on that day will be used.

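### The SAP-defined weekly itch score (PP-NRS) cannot be obtained as an off-treatment average at Week 9, because diaries are collected at Week 8 and not re-issued

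*SAP*

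**What the plan says.** **Weekly score.** SAP 10.4 states: "Average weekly PP-NRS scores will be calculated for all nominal visits". Each is the mean of seven daily post-baseline scores up to and including the visit day. The missing-data condition reads "If daily PP-NRS scores are missing for more than 3 days in a 7-day period"; the weekly score is then missing, so at least four daily scores are needed. Protocol 10.4.2.2 gives the same seven-score definition and makes no exception for Week 9.

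**Week 9.** SAP 7 lists Week 9 (Day 64) in its visit table, and SAP 10.4 adds: "Missing data at the Week 9 Follow-up visit will be summarized as OC only". Some Week 9 output is therefore expected. Protocol Table 1 and 7.8 schedule a PP-NRS at that visit. Protocol 6.2.2.3 says that on visit days the score is taken in the clinic and refers to the preceding 24 hours. Attendance is restricted: "Subjects who complete Visit 6/Week 8 but do not enroll in the OL-LTE study will return to the study site at Week 9".

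**Diary.** Daily scores between visits are recorded in the diary. The Table 1 row "Dispense (D)/collect (C) diary" shows dispensing at Baseline, collection with re-dispensing at Weeks 1, 2 and 4, collection alone at Week 8, and nothing at Week 9. The visit lists agree. Protocol 7.3 to 7.5 each include a dispensing step. Protocol 7.6 has only "Collect subject diaries" and a compliance review. Protocol 7.8 has no diary step.

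**The concern.** The missing-day rule is there to deal with subjects who fill in the diary poorly. At Week 9 the schedule itself creates the gap, because nobody has a diary to fill in.

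Two things follow. For most combinations of visit days the weekly score is missing by design. And because Week 9 is reported as observed cases, the only values that survive come from subjects whose two visits fall unusually close together. For them the value labelled Week 9 is made up mainly of days on study drug.

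Week 9 is the one visit planned for after the end of treatment, in a disease that Protocol 1.1.1 describes as intensely itchy and relapsing. It bears on the objective of describing efficacy over time. A weekly score there should either mean itch off treatment or not be calculated.

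**Working it through.** The plan states no figure for this, so there is none to reproduce. The check is a count of days.

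**Inputs**
- Week 8 visit: Day 57 ±2, so Days 55 to 59 (Protocol 7.6).
- Week 9 visit: Day 64 ±2, so Days 62 to 66 (Protocol 7.8).
- Scores after Week 8: one, in the clinic at Week 9 (Protocol 7.6, 7.8, Table 1).
- Last intended dose: the day before the Week 8 visit. Protocol 3.3 counts 56 intended doses for a Day 57 visit, and Table 1 has no application at Week 8. With 24-hour recall, the Week 8 score therefore counts as on-treatment.
- Rule: the seven days ending on the visit day, with at least four scores (SAP 10.4).
- Assumption: the diary is complete up to Week 8, which is the most favourable case.

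**Formula**

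Let g = Week 9 day − Week 8 day. The seven-day window contains:
- on-treatment scores = max(0, 7 − g)
- off-treatment scores = 1
- available = max(0, 7 − g) + 1

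The score is calculable only if 7 − g + 1 ≥ 4, that is, g ≤ 4.

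**Results over the 5 × 5 = 25 allowed day pairs**

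| Gap g (days) | Day pairs | On-treatment scores | Off-treatment scores | Absent | Weekly score |
|---|---|---|---|---|---|
| 3 | 1 (59/62) | 4 | 1 | 2 | calculable, 4/5 = 80% on-treatment |
| 4 | 2 (58/62, 59/63) | 3 | 1 | 3 | calculable, 3/4 = 75% on-treatment |
| 5 | 3 | 2 | 1 | 4 | missing |
| 6 | 4 | 1 | 1 | 5 | missing |
| 7 (includes 57/64) | 5 | 0 | 1 | 6 | missing |
| 8 to 11 | 4 + 3 + 2 + 1 = 10 | 0 | 1 | 6 | missing |

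Missing: 3 + 4 + 5 + 10 = 22 of 25. Calculable: 1 + 2 = 3 of 25. No pair gives a valid weekly mean made up of off-treatment days.

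**Alternative reading.** If the seven scores were the last seven recorded, rather than those of seven calendar days, Week 9 would hold 6 on-treatment scores and 1 off-treatment score (6/7 = 86% on-treatment). That reading does not rescue the measure.

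**What is still available.** Every row has one off-treatment score, the Week 9 clinic value.

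**The case against.** The strongest reply is that little depends on this.

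- **Endpoints.** The only visible itch efficacy endpoint is at Week 8, when the diary is still in use. Every item in the SAP 10.7 test sequence is also at Week 8. This stands in full.
- **The rule as safeguard.** In most day pairs it declines to produce a value instead of producing a misleading one. This stands for 22 of the 25 pairs but not for the other 3.
- **Selection.** Only subjects who complete Week 8 and do not enter the OL-LTE attend Week 9. Even a complete diary there would give no randomized comparison of lasting effect. This stands, and it limits what any Week 9 itch summary can claim.
- **Text not visible.** The exploratory endpoints, SAP 11.3 and the table list in Appendix C are not shown in the public documents. A single-day or daily PP-NRS summary may be planned there. This stands as a limit on what can be said about the final report. It does not change the SAP 10.4 rule as written.
- **Unscheduled visits.** Protocol 7.10 allows diaries to be dispensed at them, but that is not routine.

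A reader might go further and infer that off-treatment itch cannot be reported at all. The documents do not support that: the Week 9 clinic score is scheduled, and Protocol 10.1 lists all efficacy data by subject. Off-treatment vIGA-AD, EASI and %BSA are also collected at that visit (Protocol 7.8). Nor do the documents say that the few calculable values would be presented as lasting itch relief.

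**Conclusion.** The point holds for the weekly average only. At target timing the SAP-defined Week 9 score is missing, with 1 of 7 scores available. It is missing in 22 of 25 allowed day pairs and is 75% to 80% on-treatment in the other 3. The result at target timing needs no assumption about how visit days are distributed. The 22-of-25 count should not be read as the share of subjects affected, because the documents give no distribution of visit days.

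The conclusion rests on no diary being issued between Week 8 and Week 9 and on the Week 8 visit-day score counting as on-treatment.

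The impact is small: a descriptive summary in a selected subset, with the primary and secondary endpoints and their tests untouched. It is worth correcting because a stated rule fails as written and the data for a usable replacement are already scheduled.

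**What to change.** **Main change, SAP only.** In SAP 10.4, exempt Week 9 from the seven-day averaging rule. Summarize the single in-clinic Week 9 PP-NRS, labelled as a one-day score, alongside the single-day Week 8 clinic score in the same subjects. State that the summary is descriptive and covers completers who do not enter the OL-LTE. Because Protocol 10.4.2.2 gives the seven-score definition without a Week 9 exception, record the departure in SAP 14, which currently reports no changes. The cost is a sentence or two and a table label, with no new data collection.

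**Optional, only if the protocol is being amended for other reasons.**
- Dispense a diary at Week 8 to subjects who will return at Week 9. Enrollment in the OL-LTE is settled at that visit (Protocol 7.6), so these subjects can be identified.
- Build the Week 9 mean only from days after the Week 8 visit. With full completion, a gap of 7 days or more gives 7 off-treatment scores. Gaps of 6, 5, 4 and 3 days give 6, 5, 4 and 3.
- State the minimum number of days for short gaps, because a 3-day gap would still be missing under the four-score requirement.

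This option costs more. It changes Table 1, 7.6 and 7.8, and Protocol 11.2.1 requires submission and approval before implementation. The present diary also records application time, so an itch-only page may have to be prepared.

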10.5 Interim Analysis and Data Monitoring

No interim analysis is planned for this study.

10.6 Examination of Subgroups

The primary and all secondary efficacy endpoints will be summarized descriptively in each baseline vIGA-ADTM subgroup, study center, age cohort (2-6 yrs, 7-11 yrs, 12-17 yrs, and \geq 18 yrs), sex, race (White, Asian, Black or African American and Other), duration of disease (\leq 2yrs, 2-5 yrs, \geq 5 yrs), prior AD medication, baseline %BSA affected (\leq 10% and \geq 10%), and country (US and Canada). The %BSA Affected continuous outcome will be further explored with summaries of change and % change in %BSA affected at Week 8, by body region. The implications of any significant heterogeneity on the assessment of overall efficacy will be explored.

10.7 Multiple Comparison/Multiplicity

Multiple comparisons of the secondary endpoints will be controlled using the Fixed-Sequence method. Hypotheses testing for the secondary efficacy endpoints will only be conducted if the primary efficacy endpoint has demonstrated statistical significance at 0.05 two-sided in favor of tapinarof. Testing of the secondary endpoints will be performed sequentially following the below pre-specified order (see details in Section 11.2) using the MI estimand analyses:

- Proportion of subjects with ≥75% improvement in EASI from Baseline at Week 8
- Mean change in %BSA affected from Baseline at Week 8
- Proportion of subjects with $\geq 90\%$ improvement in EASI from Baseline at Week 8
- Proportion of subjects ≥12 years old with a Baseline PP-NRS score ≥4 who achieve ≥4-point reduction in the average weekly PP-NRS from Baseline at Week 8

Hypothesis testing for secondary endpoints will stop if statistical significance at 0.05 two-sided in favor of tapinarof is not observed.

10.8 Multicenter Studies

There will be approximately 60 study sites in the United States (US) and Canada.

The primary and secondary efficacy endpoints will be summarized by study site using descriptive statistics. Exploratory analyses of the primary and secondary endpoints may be performed to elucidate any identified sources of heterogeneity in the results.

11. METHODS OF EFFICACY ANALYSIS

11.1 Primary Efficacy Analyses

The primary estimand of interest is the composite estimand in a patient population offered treatment with tapinar fcream, 1% as compared to vehicle. Interest is focused on the treatment

effect measured by the ratio of response rates at Week 8. The primary efficacy endpoint for treatment effectiveness is proportion of subjects who achieve vIGA-ADTM score of clear (0) or almost clear (1) and at least a 2-grade reduction from Baseline at Week 8. Subjects who prematurely discontinue treatment due to an AE or lack of efficacy and subjects who use a prohibited medication with significant impact on efficacy evaluations prior to Week 8 will be considered treatment failure as of the start of the intercurrent event. Discontinuing treatment due to adverse event or lack of efficacy will be based on data recorded on the End of Treatment eCRF. Analysis will be based only on data collected at in-person visits for investigator assessments.

Estimand Attribute	Description
Treatment	tapinar of cream, 1% compared to vehicle
Population	Intent-to-treat
Variable of interest	Proportion of subjects who achieve vIGA-AD TM score of clear (0) or almost clear (1) and at least a 2-grade reduction from Baseline at Week 8
Intercurrent event handling	Subjects who prematurely discontinue treatment due to an AE or lack of efficacy and subjects who use a prohibited medication with significant impact on efficacy evaluations prior to Week 8 will be considered treatment failure. Investigator assessments will only include data collected at inperson visits.
Summary measure	Ratio of response rates at Week 8

The primary efficacy comparison will test the following hypotheses:

- H₀: The proportion of subjects who achieve a vIGA-ADTM score of clear (0) or almost clear (1) and at least a 2-grade reduction from Baseline at Week 8 is equal between tapinar of cream, 1% and vehicle cream;
- H₁: The proportion of subjects who achieve a vIGA-ADTM score of clear (0) or almost clear (1) and at least a 2-grade reduction from Baseline at Week 8 is different between the tapinar of cream, 1% and vehicle cream.

The primary efficacy endpoint will be analyzed using a Cochran–Mantel–Haenszel (CMH) test stratified by vIGA-ADTM score at Baseline (vIGA-ADTM scores of 3 or 4) and age group (2-6 yrs, 7-11 yrs, 12-17 yrs, 18+ yrs) based on the ITT population using the MI estimand approach.

- For each of the 100 multiple imputation datasets, the CMH option in PROC FREQ will
 calculate the adjusted estimate of the common relative risk of achieving a vIGA-ADTM
 score of clear (0) or almost clear (1) and at least a 2-grade reduction from Baseline at
 Week 8 (tapinarof/vehicle) over all strata with the corresponding 95% confidence interval
 (CI).
- The logit-based version of the estimates and confidence bounds will be log-transformed and the SE of the estimate of the log (relative risk) will be back-calculated from the log (confidence bounds) by assuming an asymptotic normal distribution.

- The estimates of the log (relative risk) and their standard errors for all the multiple imputation datasets will be input to PROC MIANALYZE to test the null hypothesis that tapinarof is not different from vehicle. The p-value of the combined results will be reported for interpretation.
- PROC MIANALYZE will output an overall estimate of the log (relative risk) and 95% CI. These will be exponentiated to produce an overall estimate of the relative risk and 95% CI.
- The treatment difference in mean proportion of subjects who achieve a vIGA-ADTM score of clear (0) or almost clear (1) and at least a 2-grade reduction from Baseline at Week 8 will be computed along with the 95% CI.

Sensitivity analyses in the ITT population will be conducted in which missing values are not imputed (i.e., OC), are imputed as TFs, imputed using LOCF, or imputed using the MI non-estimand approach. For the MI non-estimand analyses, efficacy will be tested as described above for the MI estimand approach. For the other sensitivity analyses, efficacy will be tested using a CMH test stratified by vIGA-ADTM score at Baseline and age group.

Additional sensitivity analyses of the primary endpoint (in addition to MI non-estimand, LOCF, OC, and TF as specified in section 10.4) will be done as follows:

• tipping point analysis

A tipping point analysis will be done using vIGA-ADTM observed cases data. All possible combinations of the number of imputed successes (vIGA-ADTM score of clear (0) or almost clear (1) and at least a 2-grade reduction from Baseline at Week 8) by treatment group will be enumerated, accounting for baseline vIGA-ADTM and age group. CMH p-values will be computed for each combination and results will be summarized and displayed in a tipping point plot. If computational issues are encountered due to a large number of combinations, then alternative approaches will be utilized.

Supporting analyses of the primary endpoint will also be performed:

• in the PP population using the MI estimand dataset only.

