5.2 Randomization/Treatment Assignment

For the double-blind, vehicle-controlled phase of the study, subjects will be randomized at a ratio of 2:1 to receive tapinarof cream, 1% or vehicle cream as follows:

Randomization in Double-Blind, Vehicle-Controlled Phase	
Regimen	Number of Subjects
Tapinarof cream, 1% QD for 8 weeks	Approximately 267 Subjects
Vehicle cream QD for 8 weeks	Approximately 133 Subjects

QD = once daily

Randomization will be stratified by Baseline vIGA-AD™ score so that subjects with severe AD (vIGA-AD™ score of 4) will be limited to approximately 10% each of the total randomized population, and the majority of the enrolled subjects (approximately 90%) will have a vIGA-AD™ score of 3, signifying moderate disease.

Randomization will also be stratified by age so that a minimum of approximately 15% of subjects will be enrolled into each of the following age groups: 2-6 years, 7-11 years, 12-17 years, 18 years and above. Adults 18 years and above will comprise a maximum of 20% of enrolled subjects.

The randomization lists will be generated using a validated system, which involves a pseudo-random number generator so that the resulting treatment will be both reproducible and non-predictable. Access to the codes will be controlled and documented.

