10.4.2.2 Secondary and Exploratory Efficacy Endpoint Analyses

The secondary efficacy endpoints are as follows:

- Proportion of subjects with $\geq 75\%$ improvement in EASI from Baseline at Week 8
- Mean change in %BSA affected from Baseline at Week 8
- Proportion of subjects with $\geq 90\%$ improvement in EASI from Baseline at Week 8

- Proportion of subjects ≥ 12 years old with a Baseline PP-NRS score ≥ 4 who achieve ≥ 4 -point reduction in the PP-NRS from Baseline at Week 8

Exploratory efficacy endpoints are as follows:

The same methods as discussed for the primary analysis of the primary endpoint will be used to analyze all dichotomized secondary endpoints. The secondary efficacy endpoints will be tested sequentially in the order listed. Testing will stop if non-significance (2-sided $p \geq 0.05$) is observed.

Post-baseline weekly PP-NRS scores will be an average of 7 daily post-baseline PP-NRS scores prior to and including the values assessed on the visit date.

Other efficacy endpoints will be analyzed using CMH test for proportions, and analysis of covariance (ANCOVA) model for continuous variables. CMH tests will be stratified by Baseline vIGA-AD™ score and age group, and ANCOVA models will include vIGA-AD™ score and age group as categorical covariates and Baseline as a continuous covariate.

All endpoints will be summarized descriptively as follows: continuous data will include the mean, SD, minimum, maximum, median, and number of observations; descriptive summary statistics for categorical data will include frequency counts and percentages.

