5. DETERMINATION OF SAMPLE SIZE

It is estimated that the proportion of subjects who will achieve a vIGA-ADTM score of 0 or 1 and at least a 2-grade reduction from Baseline to Week 8 will be 45% for subjects receiving tapinarof compared with 25% for subjects receiving vehicle control, based upon the Phase 2 results. With 400 subjects randomized in a 2:1 ratio (267 subjects receiving tapinarof, and 133 subjects receiving vehicle control), this will provide 97.2% power for statistical significance (2-sided p <0.05). The power is calculated from a Fisher Exact sample size calculation. It is assumed that 15% of the subjects receiving tapinarof will be lost to follow-up by 8 weeks compared with 30% of the subjects receiving vehicle control. These subjects will be included in the primary analysis using the multiple imputation method.

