14. CHANGES TO PROTOCOL-SPECIFIED ANALYSES

Not applicable. There are no changes to the protocol-specified analyses.

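### The deciding primary p-value is a Wald test on the logit common relative risk, not the named CMH test; it understates tapinarof's effect and costs about 4 to 8 points of power

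*SAP*

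**What the plan says.** SAP 11.1 and Protocol 10.4.2.1 both name a Cochran-Mantel-Haenszel test; in the SAP it is a "test stratified by vIGA-ADTM score at Baseline (vIGA-ADTM scores of 3 or 4) and age group". Two severity levels by four age groups give eight strata. The declared summary measure is the ratio of response rates at Week 8.

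The steps listed in SAP 11.1 use the CMH option of PROC FREQ to obtain a common relative risk in each of the 100 imputed datasets. Then "The logit-based version of the estimates and confidence bounds will be log-transformed", the standard error is recovered from the log confidence limits, and both go to PROC MIANALYZE. "The p-value of the combined results will be reported for interpretation". The CMH statistic itself is never combined.

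Other places that bear on this:
- SAP 11.1, for observed cases, treatment failure and LOCF: "For the other sensitivity analyses, efficacy will be tested using a CMH test stratified by vIGA-ADTM score at Baseline and age group". The tipping point analysis also uses CMH p-values.
- SAP 5 gives 97.2% power: "The power is calculated from a Fisher Exact sample size calculation".
- Protocol 10.4.2.2: "The same methods as discussed for the primary analysis of the primary endpoint will be used to analyze all dichotomized secondary endpoints".
- SAP 14: "There are no changes to the protocol-specified analyses".
- Protocol 5.2 says that "subjects with severe AD (vIGA-AD™ score of 4) will be limited to approximately 10% each of the total randomized population", whereas the Synopsis makes 10% a minimum.

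**The concern.** The test that decides the trial is neither the one named nor the one behind the stated power. The logit version pools stratum log relative risks with inverse-variance weights estimated from the same responses. In small strata, weight and estimate are then correlated. Under 2:1 allocation the vehicle arm contributes most of the variance, so a chance excess of vehicle responders both lowers a stratum's relative risk and raises its weight. The pooled estimate is pulled down whether or not there is a treatment effect.

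At 10% severe, the four severe strata hold about 5 to 7 tapinarof and 3 to 4 vehicle subjects each. The SAP gives no rule for a stratum with no responder in one arm.

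A missed primary stops all testing of secondary endpoints (SAP 10.7), and the dichotomized secondaries inherit the method. The sensitivity analyses that use plain CMH can also differ from the primary because of the test rather than the missing-data rule they are meant to probe.

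**Working it through.** **Inputs from the documents.** 267 and 133 subjects, 45% versus 25% (relative risk 0.45/0.25 = 1.80), two-sided 0.05, eight strata, about 10% severe, at least about 15% in each age group, adults at most 20%.

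**Assumptions.** Age mix 28/27/25/20% and 2:1 within strata, giving tapinarof 67/7/65/7/60/7/48/5 and vehicle 34/4/32/4/30/3/24/3 (moderate then severe within each age group; rounding makes the totals 266 and 134). Zero-event strata are handled two ways: 0.5 added, or stratum dropped.

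**Stated power.** Exact enumeration of two-sided Fisher power at 267 versus 133 gives 97.6%, and the continuity-corrected normal formula gives 97.3%. The SAP's 97.2% reproduces for the test it names.

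**Formulas.** For stratum h:
- Logit: log RR = Σ w_h log RR_h / Σ w_h, with 1/w_h = (1−p1_h)/x1_h + (1−p0_h)/x0_h, where x is the observed number of responders in the arm and p the observed proportion.
- Mantel-Haenszel: RR = Σ(x1_h n0_h/N_h) / Σ(x0_h n1_h/N_h), with its standard log-scale variance.

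**Mechanism.** Take the 67 versus 34 stratum at the planned rates. Tapinarof contributes 0.55/30.15 = 0.018 to the variance and vehicle 0.75/8.5 = 0.088, so vehicle supplies 83%. Now take two such strata, tapinarof at 45% in both, with 12 and 5 vehicle responders of 34 (together 17/68 = 25%):
- 12 responders: RR = 0.45/0.353 = 1.275; weight = 1/(0.0182 + 0.0539) = 13.9.
- 5 responders: RR = 0.45/0.147 = 3.06; weight = 1/(0.0182 + 0.1706) = 5.3.

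The low-RR stratum gets 2.6 times the weight. The logit pooled RR is exp[(13.9 × 0.243 + 5.3 × 1.118)/19.2] ≈ 1.62. The Mantel-Haenszel value is 0.45/0.25 = 1.80.

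**Sparse strata.** At 25% response, the chance of no vehicle responder is 0.75⁴ = 32% with 4 vehicle subjects and 0.75³ = 42% with 3.

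**Simulation.** 200,000 complete-data trials per scenario, equal response across severity:

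| | Logit, +0.5 | Logit, dropped | MH RR | CMH |
|---|---|---|---|---|
| Power, 45% vs 25% | 91.9% | 89.7% | 97.5% | 97.9% |
| Geometric mean RR (true 1.80) | 1.66 | 1.64 | 1.82 | – |
| 95% CI coverage | 91.3% | 90.2% | 95.1% | – |

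The loss against Mantel-Haenszel is 97.5 − 91.9 = 5.6 points, or 97.5 − 89.7 = 7.8. With 0.5 added, CMH is significant and the primary test is not in 6.0% of trials; the reverse did not occur.

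**No effect (25% in both arms).** Logit with 0.5 added: RR 0.96, upper tail 0.7%, lower tail 3.7%. Mantel-Haenszel: RR about 1.00, tails 2.1% and 2.8%. With 1:1 allocation the logit RR returns to 1.00, so the shift under no effect comes from the 2:1 ratio.

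**Variations, loss against Mantel-Haenszel over both zero-cell rules.**
- Severe subjects respond less (31/15%, 25/14%, 25/7% or 15/5%, overall held at 45/25%): 3.7 to 6.3 points.
- 20% severe: 4.1 to 8.3 points (for example 90.7% versus 97.5%).
- Moderate strata alone: 92.2% versus 96.0%, so sparse strata are not the whole cause.
- Four severe strata merged into one: 94.1% versus 97.5%.

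A separate simulation with a more even age mix (26.7/26.7/26.7/20%) and fixed or blocked allocation gave losses against CMH of about 3 to 8 points with 0.5 added.

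**Missing data.** With 15%/30% dropout, 100 imputations and 0.5 added, 12 scenarios (visit correlation 0.5 to 0.85) gave losses of 7.7 to 12.1 points with no treatment-failure rule, and 4.4 to 6.6 if half of dropouts are set to failure. Two scenarios rerun with 6,000 trials gave 79.3% versus 90.9% and 91.8% versus 96.7%. A separate 1,000-trial check without failures gave 85.2% versus 94.6%.

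**The case against.** The method is written out step by step before unblinding, so nobody can doubt which p-value decides. Protocol 10.6 already says the results will be converted to a normal statistic and combined in PROC MIANALYZE, and the estimand is a ratio of response rates. On that reading SAP 11.1 implements the protocol, and SAP 14 is not plainly false. This has force, but the protocol wording permits pooling a relative risk without requiring the logit version. A Wald test on the Mantel-Haenszel RR is not the CMH statistic either. Changing the estimator and naming the deciding test are therefore separate repairs, and both are needed.

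The error is also conservative: false claims of benefit fall below 2.5%, complete-data power stays near 90%, and the sponsor bears the cost. That is true and limits the severity. It does not rescue the estimate or its interval.

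The loss depends on the planned rates. At 45% versus 20% it is only 0.7 points (99.2% versus 99.9%), although the RR is still understated. If severe subjects almost never respond, it falls to about 3. The zero-cell rule is whatever PROC FREQ applies, which the documents do not state, so the figures for dropped strata are one of two possibilities. With strata dropped, the reverse discordance does occur, in 0.0075% of trials. The missing-data figures rest on assumed visit correlations and fewer trials, and deserve less weight than the complete-data ones.

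**Conclusion.** The concern holds. The primary p-value is a Wald test on the logit common relative risk. At the planned 45% versus 25% with complete data it loses about 4 to 8 points of power against the Mantel-Haenszel RR. The chance of missing the primary rises from about 2.5% to between 8.1% and 10.3% in the base case. The reported RR averages about 1.65 instead of 1.80, and its interval under-covers. The stated 97.2% does not describe the test used.

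The direction held under every age mix, severe share, severe response rate and zero-cell rule tried at 2:1 allocation; the size depends on those assumptions. Type I error in favor of tapinarof is not inflated, so this should be fixed but does not threaten the validity of a positive result. The documents give no secondary response rates, so no secondary power is claimed.

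**What to change.** Before unblinding (SAP 6 treats later changes as post hoc):
1. In SAP 11.1, replace the logit version with the Mantel-Haenszel common relative risk and confidence limits from the same PROC FREQ output. Keep the log transformation, the standard error step and PROC MIANALYZE.
2. State in SAP 11.1 that this test gives the primary p-value, and list it in SAP 14. It disagreed with CMH on significance in only 0.4% of simulated trials.
3. Apply the same to EASI75, EASI90 and PP-NRS response. PP-NRS is limited to age 12 and above, so it has at most four strata.
4. In SAP 5, give power for the test actually used.

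The cost is a short SAP amendment and one changed output line in the program; no new data are needed. Upper-tail error under the null becomes 2.1%, still below 2.5%.
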